### **Research Method and Design:**

A randomized control trial was used as research method on indoor residential patients and guidelines of good clinical practices were followed (Guideline, 2001). The sample size for this clinical trial was 60 in total (30 for control group and 30 for treatment group) in order to maintain this number, the sample size was extended to 34 for each group in order to get adequate retention of the sample. The retention number of sample was 68 at the time of pre assessment and closed at 59 at the time of last follow up assessment. All participants who were admitted for treatment of SUD with or without comorbid mental disorders were recruited for research. Intervention was administered after the 21 days of detoxification. For recruitment and randomization, it was not applicable to control extraneous variables in a single facility so two sites were selected for this purpose. Selection of sites were based on minimizing extraneous variables by selecting identical residential treatment sites. One site such as Islamabad Rehab Clinic (IRC) was willing to give permission for implementation of IICRA based intervention. Hence, IRC was selected for recruiting treatment group.

Second site was considered for recruiting control group where they were giving traditional treatment in residential setting based on disease model. The site is named as Hayat Rehab Clinic (HRC). The permission for conducting research and recruiting participants were sought out from the authorities. Traditional treatment was termed as treatment as usual which includes detoxification of drugs and duration of detoxification from acute withdrawal consisted on 21 days,

During these early days focus was on adjustment to residential treatment along with hygiene and routine related compliance. Afterwards, the focus was on general counselling for drug addiction prevention, twelve steps program, habit formation based on seven habits for highly effective people and life skills training which is mainly delivered through group classes and lectures. Patients' individual sessions are also scheduled with psychologists once weekly, the focus of these individual sessions is to maximize the interaction with family through relationship building and relapse prevention skills. Duration of residential treatment is between 90-120 days.

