The treatment group received interventions based on Islamically Integrated CRA (IICRA). These sessions were divided into daily goals including counseling related to hygiene, physical activities, psychotherapy of mental disorders and drug addiction related management. After discharge from residential treatment, they were followed up for six months to check the effectiveness of IICRA in the context of relapse and recovery from SUD as well as from comorbidities. These six months follow up was consist of further three follow up sessions; first session was conducted on the discharge date from the facility, second was on fifth month and third was on sixth month following discharge.

Sample in the present study for clinical trial was based on those diagnosed individuals who were hospitalized in rehab for the treatment of SUD. Age of the sample was varying from 16 years to 60 years, where 24% individuals were from late adolescence, 39% from early adulthood and finally 37% were from middle adulthood. The chronicity of disease in the sample varies 78% of them were abusing substance between from one year to 10 years and 22% were abusing more than 10 years. Similarly, the rate of relapse or number of treatments within sample was computed as 54% individuals were hospitalized first time and 46% were hospitalized two and more than two times. Additionally, the type of substance abuse was also varying cross the

sample which included cannabis, alcohol, pills, heroin, Ice and multiple substance abuse (Alcohol, cannabis and prescribed substances) as well. The gender was mainly male in sample which was 98% and only one participant was female in the sample. Moreover, 75% individuals of the sample were diagnosed with SUDs and 25% were also having comorbid mental illness. Hence, the representativeness of the sample was limited to clinical population diagnosed with SUDs as well as comorbidities with SUDs.

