Secondly, the professionals who were providing treatment were not aware of the allocation of the individual in control and treatment group as well as the recruited individuals for the clinical trial. They were responsible for conducting sessions and recording those sessions through treatment forms as well as monitoring the goals whether desired goal is achieved or not. They were also given the treatment protocol schedule for effective treatment adherence. Additionally, panel assessments were planned at both sites for reviewing and addressing treatment related issues faced by professionals as well as the achievement of desired goals of the treatment. These panel assessments were carried out by weekly to ensure the engagement of the patients, adherence and fidelity to the treatment protocols. This committee was comprised of four professionals having experience in the treatment planning and execution with the minimum educational level of MS in Clinical Psychology.

Moreover, for the purpose of comparability of results and to control the extraneous variables, two treatment sites were selected for clinical trial. Both sites were equal in terms of organizational structure which includes residential treatment facility for mental health, same geographical region with outdoor areas, hierarchy of professionals, daily routine of the patients, psychiatrist consultation, outdoor and indoor activities of the patients and length of residential

treatment. The professionals engaged in the clinical trial has similar qualification and experience at both facilities.

During this clinical trial, 28 out of 34 participants were retained in control group and successfully completed the duration of clinical trial. Three participants had withdrawn the treatment after 40 days of hospitalization and one individual passed away after discharge from rehab. Remaining two participants did not continue the follow up sessions.

Similarly, in experimental group 31 participants out of 34 had successfully completed the Treatment duration for clinical trial. Two participants had withdrawn the treatment after a month of admission and one participant did not continue after the discharge from the facility.

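### The sample description gives no denominator, fits the 59 completers rather than the 68 assessed at entry, and so cannot show whether the two clinics' patients were comparable at baseline

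*Protocol*

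**What the plan says.** All the Protocol text on this point is under Research Method and Design.

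- **Numbers:** "The retention number of sample was 68 at the time of pre assessment and closed at 59 at the time of last follow up assessment". Recruitment was raised from 30 to 34 per arm to allow for loss.
- **Losses by arm:** in control, "28 out of 34 participants were retained in control group and successfully completed the duration of clinical trial"; "in experimental group 31 participants out of 34 had successfully completed the" treatment. Reasons and approximate timing are given for all nine losses, but none of those patients' characteristics.
- **Sample description:** age is given as "24% individuals were from late adolescence, 39% from early adulthood and finally 37% were from middle adulthood". For duration of use, "78% of them were abusing substance between from one year to 10 years and 22% were abusing more than 10 years". First and repeat admissions are 54% and 46%, and patients without and with comorbid mental illness are 75% and 25%. The sample is 98% male, and "only one participant was female in the sample".
- **What is not stated:** the denominator, the time point, and any split by arm. Substance types are listed without percentages.
- **Source of the arms:** the treatment group was recruited at one clinic and the control group at another.

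The SAP names independent and paired t-tests and a one-way ANOVA. It defines no analysis population, no handling of missing scores and no baseline table.

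**The concern.** A reader will take a paragraph on the trial sample to describe everyone who entered, which is 68 patients. Two of its figures do not agree with 68, while all of them agree with the number who finished.

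If the description covers completers only, the nine patients who left or died are absent from the only patient-level description in the documents. That matters here for two reasons. Arm coincides with clinic, so a difference in case mix between the clinics is a direct rival explanation for any difference in outcome. The Protocol's objectives also ask about patients with and without comorbidity and about first against repeat treatment, and the make-up of those groups at entry is then unknown.

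**Working it through.** **Inputs (Protocol, Research Method and Design).** 68 at pre-assessment; 59 at last follow-up; 28/34 control and 31/34 treatment completers; age 24/39/37%; duration 78/22%; admissions 54/46%; comorbidity 75/25%; 98% male with exactly one woman.

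**Step 1: the totals agree.** 34 + 34 = 68 and 28 + 31 = 59. Losses are 6 + 3 = 9.

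**Step 2: which denominators fit?** For each N from 20 to 100, look for whole-number counts that sum to N and whose values of 100 × k/N round to every stated percentage, with one woman. Under ordinary rounding, N = 59 is the only solution, and each split has exactly one set of counts.

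| Split | Stated % | N = 59 | N = 68 |
|---|---|---|---|
| Age | 24/39/37 | 14/23/22 = 23.7/39.0/37.3 | none |
| Duration of use | 78/22 | 46/13 = 78.0/22.0 | 53/15 = 77.9/22.1 |
| Admissions | 54/46 | 32/27 = 54.2/45.8 | 37/31 = 54.4/45.6 |
| Comorbidity | 75/25 | 44/15 = 74.6/25.4 | 51/17 = 75.0/25.0 |
| Male | 98, one woman | 58/59 = 98.3 | 67/68 = 98.5, rounds to 99 |

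**Step 3: why 68 fails.**

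- Age: 26/68 = 38.2% rounds to 38 and 27/68 = 39.7% rounds to 40, so no count gives 39%.
- Sex: with one woman, (N − 1)/N rounds to 98% only for N from 40 to 66.

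The other three splits fit both sizes and do not discriminate.

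**Step 4: other plausible denominators.**

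- N = 60 (planned size) fails on age (23/60 = 38.3%, 24/60 = 40.0%) and on admissions (32/60 = 53.3%, 33/60 = 55.0%).
- N = 63 (68 less the five who withdrew from treatment) fails on age (24/63 = 38.1%, 25/63 = 39.7%).
- Truncating throughout, or rounding up throughout, fits no N from 20 to 100.

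**Step 5: size of the omission.** 9/68 = 13.2% overall; 6/34 = 17.6% in control and 3/34 = 8.8% in treatment. Fisher's exact test, two-sided, gives p = 0.48.

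**Step 6: what the nine could change.** The documents do not describe them, so only bounds are possible. Assume the 59-based counts are right, and let none or all of the nine fall in a category:

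| Category | Count among 68 | % of 68 |
|---|---|---|
| Late adolescence | 14 to 23 | 20.6 to 33.8 |
| More than 10 years of use | 13 to 22 | 19.1 to 32.4 |
| Two or more admissions | 27 to 36 | 39.7 to 52.9 |
| Comorbid illness | 15 to 24 | 22.1 to 35.3 |

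These are extreme limits, not estimates.

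**The case against.** The strongest objection is that the denominator is inferred and that loose rounding could rescue 68. Eight of the ten percentages fit 68. The sex figure is close to a tie: 98.5% could have been cut to 98. Age counts of 16/27/25 out of 68 are 23.5/39.7/36.8%, which round to 24/40/37 and sum to 101, so an author might have trimmed 40 to 39 to reach 100. A total of 67 (one record missing, which the documents do not suggest) also fits every split except sex, where 66/67 = 98.507% is another near tie.

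This stands as a reason not to call the denominator proven. It is still the weaker reading. At 68 it needs 39.7% cut down while 23.5% in the same split is rounded up, and a second downward cut for sex. The usual way of forcing a total of 100 would trim the figure with the smallest fraction, giving 23/40/37. One ordinary rule explains all ten figures at 59, a number the Protocol itself reports.

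Three further objections are fair and limit the point:

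- Attrition is disclosed by arm and reason. Only the lost patients' characteristics are missing.
- A pooled table of all 68 would also hide differences between the clinics. The split by arm is needed whatever the denominator.
- The Protocol offers other grounds for comparability: it claims randomisation and describes the two sites as alike in structure, routine, length of stay and staffing. These are not comparisons of patients, but it would be wrong to say that baseline balance is the only evidence.

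**Conclusion.** The point holds as one of reporting and of an undefined analysis set. The sample description very probably covers the 59 completers, pooled over arms, and omits 9 of 68 patients (13.2%). It therefore cannot show whether the two clinics' patients were comparable at entry. This rests on ordinary rounding and on the stated count of one woman.

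A reader might infer more than the documents support:

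- **That the percentages are wrong.** They are right for 59; what they lack is a label.
- **That the statement on representativeness fails.** It limits the sample to a clinical population with substance use disorders, with or without comorbidity, and that is true at 59 or 68.
- **That loss depended on arm.** Six against three is twofold in count but compatible with chance (p = 0.48). Equally, numbers this small cannot rule out a dependence.
- **That the outcome analysis used completers only.** A descriptive paragraph suggests this but does not show it. The SAP is silent, which is the reason to state the analysis set.

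**What to change.** 1. State the denominator of the present percentages. If it is confirmed as 59, label them as completers and leave the figures unchanged. If not, give the true denominator and the rounding used.
2. Report age group, duration of use, number of treatments, substance type and comorbidity for all 68 patients with a pre-assessment, by arm, as counts with percentages.
3. Summarise the nine lost patients in aggregate, not as a list. With one woman, one death and two named clinics, individual rows or sex by arm could identify someone; sex can stay as a pooled figure.
4. In the SAP, define the analysis set as all 68. Analyse SCL-90 and ARQ scores with a mixed model on all available assessments (arm, time, arm by time, with repeated scores linked within patient), and give the 59 completers as a sensitivity analysis. The model assumes that loss is explained by the observed data, and it does not remove the overlap of arm with clinic.

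The cost is modest: re-tabulation of data that should already exist, since 68 patients were assessed at entry, plus one added model specification and some wording.

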**ADAPTATION OF COMMUNITY REINFORCEMENT APPROACH FOR
THE TREATMENT OF DRUG ADDICTION**

[name]

74-FSS/PHDPSY/F-18

[name]

Associate Professor (supervisor)

Department of Psychology

Faculty of Social Sciences

International Islamic University Islamabad

July 10, 2024

Statistical Analysis Plan

The collected data for this clinical trial was analyzed using SPSS 25 version. Important statistical analysis includes independent sample t-test, paired sample t-tests and one way ANOVA was used. Following are the defining parameters.

Independent sample t-test

Independent sample t-test was used to understand the efficacy of the treatment program between control and experimental groups.

Paired sample t-test

Paired sample t-test was used to elaborate the differences between the level of assessment. In order to assess the differences on pre and post assessment of interventions based on SCL-90 (scale of comorbidity).

One way ANOVA

One way ANOVA was used to understand the differences between pre assessment, post assessment and follow up to draw conclusion about the recovery of the participants which is measured by ARQ (Addiction recovery questionnaire).

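### Arm follows clinic, yet recorded patient case mix is neither shown by arm nor adjusted for, so the between-arm t-test is exposed to measured case-mix bias of unknown size and direction

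*Protocol*

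**What the plan says.** Under Research Method and Design, the protocol calls the study a randomised controlled trial. It then says that one clinic was chosen to supply the treatment group and a second clinic to supply the control group.

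The case for comparability comes later in the same section: "Both sites were equal in terms of organizational structure which includes residential treatment facility for mental health". The list goes on to region, staff hierarchy, daily routine, psychiatric consultation, activities and length of stay, and adds that staff qualification and experience were similar.

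The sample description in that section gives these patient factors:

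- age band: 24%, 39% and 37%
- duration of use: 78% up to 10 years, 22% longer
- previous treatment: "54% individuals were hospitalized first time and 46% were hospitalized two and more than two times"
- comorbid mental illness: 25%
- substances used, listed without frequencies

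None of these is split by arm.

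On the between-arm analysis, the SAP says only: "Independent sample t-test was used to understand the efficacy of the treatment program between control and experimental groups". It names no covariate, stratum or baseline comparison.

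**The concern.** Similar facilities do not ensure similar patients. Arm is decided by the clinic a patient entered, so any systematic difference between the two intakes goes straight into the between-arm difference and is read as treatment effect. If one clinic admits more patients with repeat admissions, long use or comorbidity, the unadjusted t-test cannot tell this apart from the intervention working or failing.

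The Objectives section itself treats poly-drug use, comorbidity and previous treatment as relevant to how well the intervention works. None of them enters the efficacy comparison, although the trial recorded them.

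**Working it through.** **Inputs from the documents.** Analysed numbers: "28 out of 34 participants were retained in control group" and "in experimental group 31 participants out of 34 had successfully completed". 28 + 31 = 59, which agrees with the protocol's statement that the sample "closed at 59 at the time of last follow up assessment". Losses are 6/34 = 17.6% in control and 3/34 = 8.8% in treatment.

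**Whom the pooled percentages describe.** I looked for whole-number counts that round to the stated percentages.

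| Factor | Counts out of 59 | Fits 68? |
|---|---|---|
| Age band 24/39/37% | 14/23/22 | No: 26/68 = 38.2%, 27/68 = 39.7% |
| Use up to / over 10 years 78/22% | 46/13 | Yes |
| First / repeat admission 54/46% | 32/27 | Yes |
| Comorbidity no/yes 75/25% | 44/15 | Yes |
| 98% male, one female | 58 male | No: 67/68 = 98.5%, which rounds to 99% |

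All five fit 59, and two cannot fit 68. The description therefore appears to cover completers only. The case mix of the 68 enrolled is not shown even in pooled form.

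**What the pooled figures allow.** The 27 repeat-admission patients could split 13/28 v 14/31 (46.4% v 45.2%, a 1-point gap) or 19/28 v 8/31 (67.9% v 25.8%, a 42-point gap). The documents cannot distinguish these.

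**Illustrative bias from one factor.** The documents give no prognostic effect, alpha or power. I assume a prognostic effect b of 0.3 to 0.8 SD, a systematic prevalence difference d between clinics of 10 to 40 points, a two-sided 5% test and no true treatment effect.

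- Bias = b × d. Smallest: 0.3 × 0.10 = 0.03 SD. Largest: 0.8 × 0.40 = 0.32 SD.
- Standard error in SD units = sqrt(1/28 + 1/31) = 0.261.
- Noncentrality = bias / 0.261. The type I error is the two-tail rejection probability of a noncentral t on 57 degrees of freedom, with within-arm SD set to 1.

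| b (SD) | d = 10 points | 20 | 30 | 40 |
|---|---|---|---|---|
| 0.3 | 0.03; 5.1% | 0.06; 5.6% | 0.09; 6.3% | 0.12; 7.4% |
| 0.5 | 0.05; 5.4% | 0.10; 6.6% | 0.15; 8.7% | 0.20; 11.7% |
| 0.8 | 0.08; 6.0% | 0.16; 9.3% | 0.24; 14.8% | 0.32; 22.6% |

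Each cell shows bias in SD, then type I error.

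**What adjustment does.** In a simulation of 8,000 runs per scenario with 28 v 31:

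| Scenario | Unadjusted: bias; type I | Adjusted for the factor: bias; type I |
|---|---|---|
| b = 0.5, d = 40 points | 0.20; 11.2% | 0.00; 4.8% |
| b = 0.8, d = 40 points | 0.32; 19.4% | 0.00; 5.1% |
| b = 0.5, d = 40 points, plus a 0.3 SD site effect | 0.50; 44.5% | 0.30; 17.0% |

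The unadjusted rates fall slightly below the first table because here the residual SD, not the whole within-arm SD, is 1. The last row shows the limit: a site effect passes through adjustment untouched.

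**The case against.** The best defence is that the sites were chosen to be alike, that one recruitment description covers both with no site-specific entry criterion, and that no figure in the documents shows the arms to differ. The last part stands. Without data by arm, one can say that the comparison is exposed to bias, but not that bias is present, how large it is or which arm it favours. The rest does not answer the point: a shared admission description does not make two clinics' intakes alike, and the protocol describes no matching of patients.

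A reader might try to size the problem from chance imbalance. With 28 v 31, the 95% limits on the difference in share are 25 points for repeat admission, 21 for use over 10 years and 22 for comorbidity (1.96 × 0.130, 0.108 and 0.113). At an assumed 0.5 SD each, the sum is 0.5 × (0.255 + 0.212 + 0.221) = 0.34 SD. That inference fails twice:

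- Chance imbalance averages to zero and is already covered by the t-test's standard error. In simulation of this setting the plain test rejected 5.2% of the time.
- The sum needs all three limits to be reached together in one direction. For independent factors the joint 95% limit is 0.5 × 1.96 × sqrt(0.130² + 0.108² + 0.113²) = 0.20 SD, and a shift of 0.34 SD or more has probability about 0.0007.

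The real concern is systematic difference between clinics, and the documents do not give its size.

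Two further objections stand as limits. Part of any prognostic effect will already be in the pre-assessment score, so the gain from adding the other factors to a baseline-adjusted model may be smaller than the illustration suggests. And adjustment is secondary to the larger problem that arm and site coincide.

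**Conclusion.** The concern holds as exposure to bias. Comparability is argued only from site and staff features, recorded patient factors are shown only pooled and apparently only for completers, and the between-arm test uses none of them. Under the stated assumptions (one factor, 0.3 to 0.8 SD, 10 to 40 points, 28 v 31, two-sided 5%), the bias ranges from negligible (0.03 SD, type I error 5.1%) to serious (0.32 SD, 22.6%). These are scenarios, not estimates.

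A reader might also infer that one regression repairs the comparison. The documents do not support that either: each clinic supplied one arm only, so no model on these data can separate the treatment effect from a site effect or from unmeasured case mix. The measured part is worth removing because the data are in hand and the cost is small.

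**What to change.** 1. Tabulate age band, years of use, previous treatment, substance, comorbidity and the pre-assessment ARQ and SCL-90 scores by arm, with standardised differences. Do this for all 68 enrolled where the item was recorded, and for the 59 completers.
2. Replace the t-test as the main between-arm analysis with a linear model of the outcome on arm, the matching pre-assessment score, previous treatment (yes/no), use over 10 years (yes/no), comorbidity (yes/no) and age group. Show the unadjusted t-test beside it. The SAP is written in the past tense, so label the model post hoc if it is added after the data were seen.
3. State that arm and site are the same variable, so that adjustment removes only measured case mix and cannot separate a site effect or unmeasured case mix from the treatment effect.

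The cost is one table, one regression on collected data and one sentence of limitation. The covariates use about 6 degrees of freedom (1 each for the score and the three yes/no factors, 2 for three age bands), leaving 59 − 8 = 51 residual degrees of freedom against 57 for the t-test.
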